11.3	Annual progress report.....	34
11.4	Public disclosure and publication policy.....	34
12.	STRUCTURED RISK ANALYSIS.....	36
12.1	Potential issues of concern.....	36
12.2	Synthesis	39
13.	REFERENCES	40

LIST OF ABBREVIATIONS AND RELEVANT DEFINITIONS

ABR	ABR form, General Assessment and Registration form, is the application form that is required for submission to the accredited Ethics Committee (In Dutch, ABR = Algemene Beoordeling en Registratie)
AE	Adverse Event
AR	Adverse Reaction
CA	Competent Authority
CCMO	Central Committee on Research Involving Human Subjects; in Dutch: Centrale Commissie Mensgebonden Onderzoek
CPC	Cerebral Performance Categories scale
CV	Curriculum Vitae
DSMB	Data Safety Monitoring Board
EU	European Union
EudraCT	European drug regulatory affairs Clinical Trials
GCP	Good Clinical Practice
GCS	Glasgow Coma Scale
IB	Investigator's Brochure
IC	Informed Consent
IMP	Investigational Medicinal Product
IMPD	Investigational Medicinal Product Dossier
LVAD	Left Ventricular Assist Device
METC	Medical research ethics committee (MREC); in Dutch: medisch ethische toetsing commissie (METC)
(S)AE	(Serious) Adverse Event
SPC	Summary of Product Characteristics (in Dutch: officiële productinformatie IB1-tekst)
Sponsor	The sponsor is the party that commissions the organisation or performance of the research, for example a pharmaceutical company, academic hospital, scientific organisation or investigator. A party that provides funding for a study but does not commission it is not regarded as the sponsor, but referred to as a subsidising party.
SUSAR	Suspected Unexpected Serious Adverse Reaction
WBP	Personal Data Protection Act (in Dutch: Wet Bescherming Persoonsgegevens)
WMO	Medical Research Involving Human Subjects Act (in Dutch: Wet Medisch-wetenschappelijk Onderzoek met Mensen)

SUMMARY

Rationale: Approximately half of all comatose patients after cardiac never regains consciousness because of severe postanoxic encephalopathy. The other half may be left with cognitive or motor disturbances. Currently, there is no treatment to promote cerebral recovery. Treatment with acyl-ghrelin improved functional recovery under experimental in vivo and in vitro conditions, and decreased histologically measured neuronal damage. Ghrelin has been tested in over one hundred human studies, including studies in healthy volunteers and patients with cardiopulmonary diseases, neuro-endocrine diseases, psychiatric diseases, and neurodegenerative diseases. Serious adverse events were extremely rare and difficult to attribute to ghrelin administration

Objective: First, we aim to measure safety and efficacy of intravenous treatment with acyl-ghrelin to promote cerebral recovery (functional outcome) in comatose patients after cardiac arrest. Second, we will study efficacy of ghrelin to modify case fatality, time to awaken, long term (cognitive) outcome, and cardiovascular outcomes, , treatment with vasoactive drugs, use of cardiac-assist devices, and cardiac biomarkers.

Study design: This will be a phase 2 multicenter, double blind, placebo controlled randomized clinical trial.

Study population: 160 comatose patients (GCS score of 8 or lower) after cardiac arrest and successful cardiopulmonary resuscitation, admitted to intensive care units of participating hospitals, will be included within 12 hours after resuscitation.

Intervention (if applicable): Intravenous treatment with acylated ghrelin 600micrg twice daily for 1 week vs. placebo.

Main study parameters/endpoints: The primary outcome measure will be functional outcome as expressed as the score of the cerebral performance category (CPC) at 6 months.

Nature and extent of the burden and risks associated with participation, benefit and group relatedness: Ghrelin has been administered as an infusion or a bolus in a variety of doses to at least 1850 study participants. At the doses evaluated in the 66 published studies with adverse event reporting, ghrelin demonstrated an excellent short-term safety profile with few adverse effects. On the other hand, the population under study is vulnerable and exact effects of Ghrelin treatment in this specific population are unknown.

Taken together, we assume the risk of an increase of morbidity or mortality is small. The remaining small risk is acceptable, given the severity of brain damage in the population under study, the insecure prognosis, and the current lack of effective treatments to improve brain recovery and functional outcome.

1. INTRODUCTION AND RATIONALE

Comatose patients after cardiac arrest have an insecure prognosis

Anoxic brain damage after cardiac arrest is one of the most common causes of coma worldwide. In the Netherlands alone, approximately 5000 patients are admitted, yearly. Epidemiologic studies have predicted a rising incidence, because of an increasing prevalence of cardiovascular risk factors and the aging population. Postanoxic encephalopathy is the most common cause of death in patients that survive cardiac arrest to hospital admission. As opposed to increased survival of cardiopulmonary resuscitation, outcome of postanoxic coma has improved only little over the past years. Despite treatment on an intensive care unit, approximately half of all comatose patients never regain consciousness as a result of severe hypoxic-ischemic brain damage.^{1,2} In the other half, there is a large probability of lasting brain damage with functional and cognitive impairments. There is limited knowledge of the pathophysiology of brain damage in postanoxic coma and hardly any insight into the severity of brain damage in individual patients.

Treatments are not available

Effective treatments to improve brain recovery in postanoxic coma are unavailable. Over the past years, there has been no substantial scientific progress. The only general treatment of presumed benefit has been cooling the brain to 32°C. This was based on evidence from two small trials in 2002. However, the benefit of cooling has become uncertain since the recent large Targeted Temperature Management trial, where cooling to 32°C was associated with the same outcome as cooling to 36°C.³ Currently, most experts believe that prevention of hyperthermia (fever) is more important than induction of hypothermia. An important rationale behind all studied, but ineffective, neuroprotective strategies, including hypothermia, has been prevention of secondary damage by inhibition of neuronal activation. The presumption is that this should preserve the remaining energy in order to maintain basic cellular processes. However, we observed that hypoxia causes wide spread inhibition of neuronal activity in itself.⁴ We established that insufficient neuronal activity during more than 24 hours is an independent predictor of absence of recovery to physiological activity patterns *in vitro*⁵ and in patients with postanoxic coma.^{6,7} This association was unrelated to the duration of the initial circulatory arrest or to the actual oxygen level. This suggests that, after the initial insult, it is not only the lack of energy, but also lack of neuronal activity, which may lead to secondary irreversible damage or recovery. None of the previously tested neuroprotective modalities by inhibition of activation were of proven benefit.⁸

Ghrelin was effective in animal models

Contrary to previous attempts, we now propose a treatment modality with mild neuronal activation. We found a massive increase of physiological neuronal activity and formation of new synapses by mild neuronal activation with Ghrelin *in vitro*.⁹ Furthermore, Ghrelin prevented apoptosis in living rats after cardiac arrest, with improved neurological recovery.¹⁰ In more than ten rat studies on focal cerebral ischemia and reperfusion (mainly by intraluminal vessel occlusion), ghrelin improved neuronal survival and functional recovery without exception, where in most studies it was assumed that ghrelin prevented apoptosis.¹¹

Ghrelin is a naturally occurring hormone and mildly excitatory neurotransmitter. The presumed mechanism of action is slowing down of apoptosis.¹²⁻¹⁵ Since hypoxia induced neuronal inactivity was independently associated with progression towards irreversible damage, both *in vitro*¹⁶ and in patients,^{6,7} we assume that the beneficial effects of ghrelin are mediated by mild neuronal activation, preventing ill-fated neuronal inactivity.⁵ This is perpendicular to the classical view of neuroprotection by inhibition, which is currently applied in all comatose patients after cardiac arrest.

Ghrelin seems safe

Ghrelin has been administered as an infusion or a bolus in a variety of doses to at least 1850 study participants, including healthy participants and patients with obesity, prior gastrectomy, cancer, pituitary disease, diabetes mellitus, eating disorders, cardiovascular disease and neurodegenerative disease (for reviews please see^{17,18}). Taken together: there is strong evidence that ghrelin stimulates appetite and increases circulating GH, ACTH, cortisol, prolactin, and glucose in various patient populations. There is a paucity of evidence regarding the effects of ghrelin on LH, FSH, TSH, insulin, lipolysis, body composition, cardiac function, pulmonary function, the vasculature, and sleep (review¹⁷).

At the doses evaluated in the 66 published studies with adverse event reporting, ghrelin demonstrated an excellent short-term safety profile with few adverse effects.¹⁷ Serious adverse events such as pneumonia, enteritis, and lung cancer were extremely rare and difficult to attribute biologically to ghrelin administration. Most of the severe adverse events derived from 1 study of ghrelin v.s placebo administration in severely ill patients with pulmonary cachexia, a group that is vulnerable to developing additional medical problems.¹⁹ Mild adverse events occurred in approximately 20% of participants receiving ghrelin. The most common effect was transient flushing, which occurred in 10% of volunteers, but resulted in discontinuation of study medication in only 3 of the 939 participants in whom adverse event collection was reported.²⁰⁻²² There was no difference in the percentage of participants experiencing flushing between bolus and infusion routes of administration.

Larger ghrelin doses may increase the risk of flushing, as indicated by the higher rate of flushing in the 2 ghrelin bolus studies that employed the largest tested dose (10µg/kg/dose). The most common gastrointestinal side effect was gastric rumbles, which occurred in 22 participants (2.3%) and was never severe enough to lead to ghrelin discontinuation. Gastrointestinal side effects and increased thirst were more common in volunteers who received continuous ghrelin infusions, perhaps due to the longer duration of exposure to ghrelin. Few participants developed neurocognitive effects including somnolence, fatigue, vertigo, or change in mood (26 subjects, 2.8%). These effects were more common in subjects who received ghrelin bolus, potentially due to the rapid ghrelin delivery.¹⁷ For more details please see investigators brochure.

First effective neuroprotective treatment in cerebral ischemia?

We propose to study the effect of ghrelin on neurological recovery of comatose patients after cardiac arrest based on the large probability of a poor outcome in this patient group, lack of effective treatments to promote brain recovery, consistent beneficial effects of ghrelin under experimental *in vitro* and *in vivo* conditions, and substantial evidence of safety.

If mild stimulation of neurons with Ghrelin provides clinically relevant improvement of recovery after hypoxic-ischemic brain damage in postanoxic coma, this will be the first identified effective treatment. This will be of large relevance for patients, families, and society given the high incidence and large impact of the disease, and the large probability of a poor outcome without adjunctive treatment. Apart from the potential clinical value, the first effective neuroprotective treatment in hypoxic-ischemic brain damage will be of conceptual value, and may be translated to other patients with cerebral ischemia, such as patients with ischemic stroke.

We know of no patents or other initiatives aiming at testing effects of ghrelin or other modalities based on neuronal activation in postanoxic coma.

2. OBJECTIVES

Primary Objective

We aim to measure safety and efficacy of intravenous treatment with acyl-ghrelin to promote cerebral recovery in comatose patients after cardiac arrest. Safety will be monitored throughout hospitalization and during follow-up using all AEs reported, and by interim analyses by an independent DSMB. Efficacy will be measured by the primary outcome measure, i.e. functional recovery as measured by the Cerebral Performance Category (CPC) scale at six months after cardiac arrest.

Secondary Objective(s):

To measure safety and efficacy of ghrelin to modify

1. Case fatality
2. Time to awaken (time interval between resuscitation and Glasgow Coma Scale (GCS) score of 14)
3. Long term outcome: CPC and cognitive functioning at 12 months
4. Cardiovascular measures:

Mean arterial blood pressure day 1-7 (mean, highest, lowest)

Heart rate day 1-7 (mean, highest, lowest)

Arrhythmia day 1-7: yes / no. If yes: type of arrhythmia

Cumulative dose of vasopressive medication day 1-7

Cumulative dose of inotropic medication day 1-7

Sequential Organ Failure Assessment score day 1-7

Kidney function day expressed as GFR day 1-7

CVVH day 1-7: yes / no

Assist devices day 1-7: yes / no

5. Biomarkers

Cardiac: troponine and CK / CK-MB ratio at day 0, 1, 2 or 3

Neurological: NSE day 1, 2, 3

Endocrinological: cortisol, growth hormone, prolactine, ACTH, IGF-1 day 1, 2, 3

Highest glucose levels at day 1-7

6. Gastro-intestinal: gastric residual volume (day 1-7, during ICU admission)

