After randomization, daily physical, neurological, and additional examinations at the ICU will be part of routine patient care. In addition, there will be blood sampling for measurement of ghrelin concentrations at day 1 and 3, measures of neuronal damage (NSE at day 1-3), measures of cardiac damage (troponine and CK/CK-MB ratio at day 0-3), hormone concentrations (cortisol, growth hormone, prolactine, ACTH, IGF-1 at day 1-3), and highest glucose levels at day 1-7. All blood samples will be collected during routine blood sampling, if possible; preferably, there will be no additional punctures. However, blood sampling for measurement of ghrelin concentrations will be done at 30±15 minutes after treatment with ghrelin or placebo. For these measurements additional blood samples will be taken, if necessary.

Apart from the study treatment and the venous blood sampling, patients will not be subjected to additional procedures during admission.

Surviving patients will be asked informed consent for participation and additional follow-up on long term outcome. Follow up at 3 and 6 months in surviving patients will be done by telephone interview by a trained research nurse three and six months after admission. The nurse will collect CPC scores based on a standard interview. At twelve months, patients will be invited to the nearest hospital or visited at their place of residence for detailed neuropsychological examination (please see F1 testbatterij NPO for details of the test

battery). Separate informed consent will be asked for neuropsychological examination at twelve months.

Table. Overview of study procedures

	Baseline (Day 0)	Day 0-6	Day 1-7	Day 7	3m	6m	12m
Ghrelin/ placebo treatment		X					
Venous blood sampling (largely within current care)	X		X				
CPC scores				X	X	X	
Neuropsychological examination							X

M = months, CPC = Cerebral Performance Category, to be collected by a telephone interview

The total burden in hours for the patient is max 12 hours. This includes multiple transfusions of the study drug, venous blood sampling, and the follow-up procedures at 3, 6 and 12 months.

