8.2.2 Adverse events (AEs)

Adverse events are defined as any undesirable experience occurring to a subject during the study, whether or not considered related to the use of Ghrelin. All adverse events reported spontaneously by the subject or observed by the investigator or his staff will be recorded. An adverse event should be reported within 10 working days to the Principle Investigator. A serious adverse event should be reported to the Principle Investigator within 24 hours of first knowledge. The following adverse events will always be reported:

- Flushing and stomach problems (mild anticipated adverse events);¹⁷
- Second cardiac arrest needing cardiopulmonary resuscitation (SAE);
- Death (SAE).

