8.2.3 Serious adverse events (SAEs)

The sponsor will report the SAEs through the web portal ToetsingOnline to the accredited METC that approved the protocol once per 2 months.

A Serious Adverse Event (SAE) is any untoward medical occurrence or effect that:

- **Results in death;**
- **Is life threatening (at the time of the event):** An event that, in the opinion of the investigator, would have resulted in immediately fatality if medical intervention had not been taken. This does not include an event that would have been fatal if it had occurred in a more severe form;
- **Requires hospitalisation or prolongation of existing inpatients' hospitalisation:** An event that results in an admission to the hospital for any length of time or prolongs the subject's hospital stay. An elective hospital admission will not be considered as a SAE.
- **Results in persistent or significant disability or incapacity:** An event that results in an unexpected (by investigators opinion) persistent or significant disability or incapacity;
- **Is a congenital anomaly or birth defect:** An anomaly detected at or after birth, or any anomaly that results in fetal loss;
- **Any other important medical event that did not result in any of the outcomes listed above due to medical or surgical intervention but could have been based upon appropriate judgement by the investigator.**

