8.4 Follow-up of adverse events

All AEs will be followed until they have abated, or until a stable situation has been reached. Depending on the event, follow up may require additional tests or medical procedures as indicated, and/or referral to the general physician or a medical specialist.

SAEs need to be reported till end of study within the Netherlands, as defined in the protocol.

8.5 [Data Safety Monitoring Board (DSMB) / Safety Committee]

The trial will be monitored by an independent data monitoring committee. The data monitoring board (DSMB) will consist of Dr. [name] (neurologist UMCU), [name] (intensivist UMCU), Dr. [name] (biostatistician LUMC), and dr. [name] (clinical pharmacologist Apotheek Haagse Ziekenhuizen en Hagaziekenhuis). The first three members of this DSMB are also involved in the TELSTAR trial (www.telstartrial.nl) and know the vulnerable population under study very well. Details on the DSMB and rules on analysis and reporting are included in K5: “DSMB charter”.

The DSMB is established to perform interim analyses for safety. Safety analyses will be performed at an individual patient level for the first ten inclusions in the trial. For these first ten inclusions, the DSMB will receive by email unblinded reports of SAEs, AEs, SUSARs, poor outcomes, and deaths after each individual inclusion. Thereby, the DSMB will have access to individual patient files. The information will be sent to the DSMB at one week \pm 3 days after inclusion (i.e. the duration of treatment). Analysis of safety in these first ten inclusions will be largely qualitative. The first ten patients will be included sequentially in one hospital (MST), where the next inclusion will only take place after a positive sign from the DSMB.

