Thereafter, the DSMB will perform safety analyses after 15, 20, 25, 50, and 100 inclusions. At that time, the DSMB will review data on SAEs, SUSARs, poor outcomes, and deaths per centre. This information will be sent to the DSMB at one week \pm 3 days after inclusion for the interim analyses at 15, 20, and 25 inclusions. For these interim analysis, the trial will only continue after a positive sign from the DSMB. For the interim analyses at 50 and 100 inclusions, the information will be sent after having reached the secondary outcome measure at three months. In addition, the DSMB will review general aspects of the trial, including patient recruitment, patient inclusion, and unexpected events. Because of the expected high proportion of patients with a poor outcome in the patient group under study, and the consequent overlap between safety endpoints and the primary endpoint, the evaluation of safety by the DSMB will be quantitative and qualitative. In addition, suspected unexpected serious adverse reactions (SUSARs) will be reported <48 hours to the METC.

The composition, tasks and responsibilities of the DSMB are described in K5: DSMB Charter.

The DSMB will advise to stop the trial at the following moments:

- A higher number of SAEs in the treatment than in the control group
- Any SUSARs
- Any other safety issues

The advice(s) of the DSMB will be sent to the Principle Investigator of the study and the METC. Should the Principle Investigator decide not to fully implement the advice of the DSMB, the Principle Investigator will send the advice to the reviewing METC, including a note to substantiate why (part of) the advice of the DSMB will not be followed.

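### SAE reporting runs through follow-up, but no post-discharge contact is scheduled to ask about SAEs, so non-fatal events after discharge may be incompletely captured

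*Protocol*

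**What the plan says.** Section 2 of the Protocol puts safety beside efficacy in the primary objective: "We aim to measure safety and efficacy of intravenous treatment with acyl-ghrelin to promote cerebral recovery in comatose patients after cardiac arrest". It gives the period and the source: "Safety will be monitored throughout hospitalization and during follow-up using all AEs reported".

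Section 8.4 sets the duration: "SAEs need to be reported till end of study within the Netherlands, as defined in the protocol". The Protocol text available for this review contains no such definition. Section 8.2.3 sets the scope. Elective admissions are excluded, but otherwise the hospitalisation criterion is "An event that results in an admission to the hospital for any length of time or prolongs the subject's hospital stay", so readmissions count.

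Section 8.2.2 says how events come to light: "All adverse events reported spontaneously by the subject or observed by the investigator or his staff will be recorded". It also lists events that must always be reported: flushing, stomach complaints, a second arrest needing resuscitation, and death. Section 8.2.1 obliges local investigators to report and has a study nurse gather all events weekly.

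Section 7.3 describes follow-up. The 3- and 6-month contacts are telephone calls, and "The nurse will collect CPC scores based on a standard interview". The 12-month contact is for neuropsychological examination. The schedule table shows CPC at 3 and 6 months, neuropsychological examination at 12 months, and no AE or SAE row.

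Section 8.5 makes a higher SAE count in the treated arm a ground for advising a stop. On timing it says: "For the interim analyses at 50 and 100 inclusions, the information will be sent after having reached the secondary outcome measure at three months".

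**The concern.** The Protocol commits to SAE capture through follow-up but describes only a passive method of finding events. In hospital that is workable, because staff see the patient every day. After discharge, the Protocol arranges contact with the patient at 3, 6 and 12 months, and no safety question is named for any of these.

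Section 1 expects a large probability of lasting functional and cognitive impairment among patients who regain consciousness. Spontaneous reporting is a weak source in such a group. A readmission, particularly to a hospital outside the trial, could go unrecorded unless someone asks about it.

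Two things are at stake: the follow-up part of the safety objective, and the non-fatal SAE data that reach the DSMB at 50 and 100 inclusions. Those two looks wait for the 3-month assessment, yet that assessment is not specified to add non-fatal SAEs. Deaths are less exposed, because case fatality at 6 months is an outcome in its own right (7.1.2).

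**Working it through.** **1. The sections side by side.**

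| Question | Protocol answer | Section |
|---|---|---|
| Is safety in follow-up in scope? | Yes, within the primary objective | 2 |
| Until when are SAEs reported? | End of study; no definition in the text available | 8.4 |
| Do readmissions count? | Yes, unless elective | 8.2.3 |
| How are events found? | Spontaneous report or staff observation | 8.2.2 |
| Who gathers them? | Local investigators and a study nurse, weekly; no post-discharge source named | 8.2.1 |
| What is named at 3 and 6 months? | CPC | 7.3 and table |
| What is named at 12 months? | Neuropsychological examination | 7.3 and table |

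The duty to report after discharge is clear. The means of learning about an event is not given.

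**2. The design figure.** Section 4.4 gives a difference of 0.8, SD 1.8, alpha 0.05 and power 80%. Per arm, n = 2(1.960 + 0.842)² × 1.8² / 0.8² = 79.5, rounded up to 80, so 160 in total. This reproduces the Protocol's figure (two-sided; power 80.3% at 80 per arm). The point does not depend on it; it only fixes the denominator.

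**3. Size of the follow-up safety set.** Section 8.2.1 gives case fatality of 50-60%.

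- Survivors in the full trial: 160 × 0.40 = 64 to 160 × 0.50 = 80, or 32 to 40 per arm.
- At the 50-inclusion look: 50 × 0.40 = 20 to 50 × 0.50 = 25, both arms together.
- At the 100-inclusion look: 100 × 0.40 = 40 to 100 × 0.50 = 50, both arms together.

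**4. What incomplete capture costs (illustration only).** The Protocol gives no post-discharge SAE rate. Assume true proportions of 20% and 40% in the two arms, and the same capture fraction s in both, so that recorded proportions are p₁ = 0.20s and p₂ = 0.40s. With n survivors per arm and p̄ the mean of p₁ and p₂:

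power = Φ{ [ |p₂ − p₁| − 1.96 √(2p̄(1 − p̄)/n) ] / √([p₁(1 − p₁) + p₂(1 − p₂)]/n) }

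For n = 32 and s = 1: (0.20 − 1.96 × 0.1146) / 0.1118 = −0.22, so power is 0.413.

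| Capture s | Expected counts, n = 32 | Power | Expected counts, n = 40 | Power |
|---|---|---|---|---|
| 100% | 6.4 vs 12.8 | 0.41 | 8 vs 16 | 0.50 |
| 75% | 4.8 vs 9.6 | 0.30 | 6 vs 12 | 0.36 |
| 50% | 3.2 vs 6.4 | 0.20 | 4 vs 8 | 0.24 |
| 25% | 1.6 vs 3.2 | 0.11 | 2 vs 4 | 0.13 |

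With equal capture the ratio between arms is preserved, the absolute difference shrinks in proportion to s, and a comparison that is imprecise even with full capture becomes weaker.

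**The case against.** The strongest reply is that the reporting duty is complete. Section 8.2.1 requires events to be reported to the sponsor and entered in the database, makes local investigators responsible, and has a nurse collect everything weekly. Section 8.2.2 says a second arrest is always reported, and section 8.4 keeps SAE reporting open to the end. It would therefore be wrong to infer that events are recorded only when a patient volunteers them, or that late events will be lost. This stands, and it is why the point is put as possible incomplete capture. But a duty operates once an event is known, and none of these sections says how it becomes known after discharge.

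Second, it is tempting to read section 7.3 as saying the calls contain CPC and nothing else. The Protocol does not say so. The content of the standard interview is not shown, and an event mentioned on a call would be recordable under 8.2.2. The schedule table is weak evidence on its own: it has no AE row even for the treatment week, and it omits the 12-month CPC listed in 7.1.2. What can be said is that CPC is the only item specified for the calls.

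Third, the practical weight is limited. Treatment lasts one week, the half-life quoted in 6.5 is 27 to 31 minutes, most deaths fall in the first week, and the looks up to 25 inclusions use data at about one week. Waiting for three months also gives the DSMB later deaths and poor outcomes. All of this is fair and keeps the point modest. It does not remove it, because the Protocol itself extends safety into follow-up.

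**Conclusion.** The point holds as a gap between what the Protocol promises and what it schedules. Sections 2, 8.2.3 and 8.4 require non-fatal SAEs, including readmissions, to be captured through follow-up. Sections 7.3 and 8.2.2 specify no enquiry that would find them after discharge. Capture may be incomplete among the 64 to 80 expected survivors, which would lower counts and precision for the follow-up part of the safety objective and for the looks at 50 and 100 inclusions. The survivor range rests on the Protocol's own case fatality; the power figures rest on assumed event rates and equal capture.

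Three stronger conclusions are not supported:

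- **Bias between arms.** A reader might infer that better-recovered patients report more, so that an effective treatment would look less safe. The Protocol gives no evidence on how reporting varies with recovery; representatives may report for dependent patients, and the argument presupposes a treatment effect. Unequal capture is possible but not shown.
- **A number missed.** Assuming that 15-30% of survivors have a late SAE and that 30-60% of these are caught would give 64 × 0.15 × 0.40 = 3.8 to 80 × 0.30 × 0.70 = 16.8 patients with unrecorded SAEs. Neither assumed range has a source in the Protocol, so this is not an estimate.
- **A missing final SAE comparison.** The by-arm safety analysis is properly left to the SAP, which is not at hand.

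The primary efficacy analysis is unaffected. This is an inexpensive improvement that should be made.

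**What to change.** - Add a short fixed set of SAE questions to the 3- and 6-month calls and the 12-month contact: any hospital admission, second cardiac arrest, or other serious event since the last contact, with dates. Put them to the representative where the patient cannot answer.
- Add an SAE row to the schedule table in section 7.3.
- State in section 8.4 when SAE collection ends, and word sections 2, 7.3, 8.2.2 and 8.4 so that they agree.

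The cost is a few minutes per contact, one eCRF page, a change of Protocol wording, and more SAE reports to process. No additional visit, staff or procedure is needed. If the standard interview already contains such questions, stating this in section 7.3 and the table covers the 3- and 6-month calls; the 12-month contact and the end of SAE collection would still need wording.
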